7. Managing or reporting of adverse events or serious adverse event, and when questions arise, in consultation with the Site Physician, Clinical Research Pharmacist, Study Chair, or Study Director.

Definitions

For CSP#590, AE and SAEs will be collected using the International Conference on Harmonisation (ICH) Clinical Safety Data Management (ICH-E2A) and CSP Global Standard Operating Procedure (SOP) 3.6.2 definitions as follows:

Adverse Events: An AE is any untoward physical or psychological occurrence in a human subject participating in research. An AE can be any unfavorable and unintended event, including an abnormal laboratory finding, symptom, or disease associated with the research or the use of a medical investigational test article. An AE does not necessarily have to have a causal relationship with the research.

Serious Adverse Events: An SAE is an adverse event that results in:

- Death
- A life-threatening experience,
- Inpatient hospitalization
- Prolongation of hospitalization,
- Persistent or significant disability/incapacity,
- Congenital anomaly/birth defect, or
- Requires medical, surgical, behavioral, social, or other intervention to prevent such an outcome.

Relatedness: Relatedness involves an assessment of the degree of causality between (or attributed to) the *study intervention* and the event. Site investigators are charged with making an assessment of relatedness based on their clinical judgment and experience. The assessment of relatedness provided by the site investigator is used by the sponsor (CSP) to determine if an AE/SAE represents an alteration or change in the safety profile of the study intervention. All AE/SAEs with a reasonable causal relationship to the investigative treatment may be considered “related”. A definitive relationship does not need to be established.

Adverse Events and Serious Adverse Events Reporting Requirements

Adverse Events: Only adverse events possibly or definitely related to the study intervention will be reported. Documentation of this assessment may be recorded on a worksheet or source document. The lithium carbonate formulation used in CSP #590 is a commercially available product prescribed for bipolar disorder. Lithium has a well characterized adverse effect profile and there is no evidence suggesting this agent will demonstrate a different adverse event profile in CSP#590 from the one already known.

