Psychiatric Diagnosis	Mini-International Neuropsychiatric Interview (Sheehan et al., 1998)	MINI	Structured interview to elicit psychiatric symptoms and determine diagnoses	Interview	Variable	Eligibility	20
	PTSD Checklist (modified to allow DSM-IV-TR and DSM-5 diagnoses); Blanchard et al., 1996)	PCL	Self-rating scale to be administered as a structured interview	Self or Interview	22	Potential covariate for exploratory analyses	6
	Substance use disorders module from Structured Clinical Interview for DSM-IV-TR Axis I Disorders (First et al., 2002)	SCID SUD	Supplementary questions related to substance use diagnoses	Interview	Variable	Eligibility	10
Cognition and Decision-Making Capacity	Orientation Memory Concentration Test (Katzman et al., 1983)	OMC	Cognitive screening instrument	Interview	6	Eligibility	6
	The Jeste Decision-Making Capacity Assessment – University of California, San Diego Brief Assessment of Capacity to Consent (UBACC)	UBACC	Evaluation of decision-making capacity	Interview	Variable	Eligibility	5

[name]: CSP#590 Lithium for the Prevention of Recurrent Suicide Attempts

Mental Health Symptoms	Patient Health Questionnaire-9 (Kroenke et al., 2001)	PHQ-9	Symptoms of depression	Self or Interview	10	Secondary Outcome	7.5
	Internal State Scale (Bauer et al., 2000)	ISS	Symptoms of bipolar disorder	Self or Interview	15	Secondary Outcome	7.5
	Alcohol Use Disorders Identification Test-C (Bradley et al., 2007)	Audit C	Quantity-frequency data on alcohol use	Interview	3	Secondary Outcome	3
Moderators	Buss-Perry Aggression Scale (Buss & Perry, 1992)	Buss Perry	Aggression as a trait	Self	29	Secondary Outcome	10
	Barratt Impulsiveness Scale (Patton et al., 1995)	Barratt	Impulsivity as a trait	Self	30	Secondary Outcome	10
Lithium side effects	Lithium side effects checklist		Systematic review of possible lithium side effects	Interview	8	Monitoring	5
Use of VA and non-VA health and mental health services (Sirey et al., 2005)	Self-report log based on the Cornell Services Index (Sirey et al., 2005)		Use of health and mental health services to include patient's report of reasons for hospitalization or emergency department visits	Log maintained by subject and reviewed by research staff at each visit	Variable	Monitoring	5 minutes for review

Table 2: Comparison of select prior studies of lithium with CSP590

	Cipriani (2005)	Guzzetta (2007)	Goodwin (2003)	Lauterbach (2008)	Oquendo (2011)	Proposed CSP590

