7.4. Safety Data

Safety information to be collected for this study include description of the event, distinction between serious and non-serious adverse event, severity and expectedness of the event, relatedness to the study intervention, and outcome of the event. In addition, data on all events will be classified using the Medical Dictionary for Regulatory Activities (MedDRA) (Version 9.0) coding dictionary.

Safety data will be collected for all consented subjects from the date the first consent was signed up to 13 months post randomization for related non-serious adverse events, and all serious adverse events. If the subject terminates from the study prior to 13 months post randomization date, collection of safety data will cease on termination date.

For reporting to the DMC and inclusion in the final report safety data will be aggregated for the ITT analytic sample only as described in **3.3**. Data will be summarized as follows.

- Frequency and percentages of related non-serious and all serious adverse events overall and by intervention group
- Frequency and percentages of all unique subjects with non-serious and serious adverse events overall and by intervention group
- Rates of non-serious and serious adverse events overall, by intervention group, and by center, calculated as # events/ person-time in years
- Tabulation of event type, MEDRA classification, severity, expectedness, relatedness and outcome of all events overall and by intervention group
- Overall hospitalization, suicide reattempt, and mortality rates at 1 year overall and by intervention group

8. Data Monitoring Committee Reports

Data and study progress will be monitored by the study executive committee and by the Data Monitoring Committee (DMC). The DMC will review the study progress and safety semi-annually with additional meetings and communications as needed. All reports will be generated using SQL and SAS.

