8.3. Outline of DMC Reports

The report is divided into four sections to cover subject disposition, baseline assessment, follow-up assessment, and safety assessment. The “Open Session” report includes summary tables that are not aggregated by treatment group (i.e., blinded data), and the “Closed Session” report includes summary tables for safety assessment that are aggregated by treatment groups (i.e., unblinded data). Following is the list of tables to be included within each of these 4 sections. Revision to this list, if any, will be discussed at the first DMC meeting to be held within six months of the initiation of subject enrollment in the VA sites.

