8.3.2. Section B: Baseline Assessment (OPEN SESSION ONLY)

Table B1. Demographics
Table B10. Study Medication Adherence
Table B11. Side Effects

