8.3.5. Section D: Safety Assessment (CLOSED SESSION ONLY)

Table D1. Rates of Non-Serious Related Adverse Events (NAEs), by Site and Treatment
Table D2. Rates of Serious Adverse Events (SAEs), by Site and Treatment
Table D3. **Reported in OPEN SESSION only**
Table D4. Summary of Serious Adverse Events (Form B15), by Treatment
Table D5. Related Non-Serious Adverse Events by System Organ Class, by Treatment
Table D6. Serious Adverse Events by System Organ Class, by Treatment
Table D7. Deaths Reported, by Treatment

9. Analytic Tables not included in the Data Monitoring Committee Reports

Following analytic tables will be generated annually and made available to the study team, Upon request of the DMC at the initial meeting these tables will not be included in the DMC report.

Table X1. Military Service

Table X2. Medical and Psychiatric History

Table X3. MINI Module Assessment

Table X4. Baseline Physical Assessments

Table X5. Baseline Laboratory Results

Table X6. Baseline Psychiatric Measures

Table X7. Baseline Substance Use (SCID-SUD)

Table X8. Concomitant Medications

10. Sample Size and Power

CSP590 is targeted to enroll a total of 1862 subjects, and approximately 40% of the enrolled sample is expected to terminate early (i.e., 20% complete data loss), thereby resulting in an analytic sample of 1490 evaluable subjects. With the evaluable study sample equally allocated to the 2 treatment arms, the study is powered to detect at least a 37% reduction in the one year outcome event rate.

Expected event rates used in sample size estimation to achieve 90% statistical power for hypothesis testing were 15% re-attempt rate in the placebo group and 9.45% re-attempt rate in the lithium group. Justification for selecting these rates to estimate sample size and power are provided in the protocol.

The results for the primary outcome measure will be analyzed by a two-sided log-rank test to detect either a hazards ratio that exceeds $1/0.61=1.64$ or is less than 0.61, i.e., the test has 90% power to detect a hazard ratio of 1.64 or larger or 0.61 or less.

These estimations are adjusted for an O'Brien-Fleming stopping rule with one interim and one final test of hypothesis, and allow for an overall two-sided type I error of 5% for the hypothesis being tested. Hence, the interim primary hypothesis will be tested at $p=0.002$ level (allowing for 0.2% Type I error), and the final primary hypothesis will be tested at $p=0.048$ level (allowing for 4.8% Type I error).

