10.2. Futility Analysis

As a part of the interim futility analysis we will estimate the conditional probability (CP) of observing a significant final result based on assumptions about the distribution of future event rates. Assumptions for additional data to be collected in the second half of the study are:

- (1) “no-change” scenario where future event rates will occur at the same rate as currently observed rates,
- (2) “expected” scenario where future event rates occur at the rates expected at the beginning of the trial (i.e., as proposed in the protocol),
- (3) “extreme” scenario where future event rates occur at the currently observed overall event rate, but all new events occur in the placebo group so as to set the best scenario for achieving a significant difference.

For conditional probability estimation, we will use the estimation method developed by Proschan, Lan, and Wittes, 2006 and further described by Jitlal et. al, 2012, where

CP at a specific time = $1 - \Phi[(Z\alpha/2 - E[B(1)|B(t)])/\sqrt{1-t}]$,

$E[B(1)|B(t)]$ is the expected value of $B(t)$ at the end of the trial (when $t=1$), given the data observed until point t .

The information fraction, t , is the number of observed events so far, expressed as a proportion of the planned number of events.

11. Final Statistical Report

The final statistical report for CSP590 will be the submitted and accepted primary manuscript which includes results from the primary ITT analysis as outlined in section 4 and any additional analyses to be conducted based on the journal's peer review process. At minimum, the final statistical report will include the CONSORT diagram (section 8.3.1), descriptive characteristics of the ITT cohort (section 8.3.2), medical and psychiatric history of the cohort (section 9), and the primary analysis results (section 4.3).

12. References

- MacKinnon, D. P.; Lockwood, C. M. Hoffman, J. M., West S. G., Sheets V. A Comparison of Methods to Test Mediation and Other Intervening Variable Effects. *Psychological Methods* 7: 83–104, 2002

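### Non-serious adverse events reach the by-arm safety analysis only if the blinded site judged them related, and the lithium side-effects checklist has no explicit by-arm output

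*Protocol*

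**What the plan says.** **The filter.** Protocol section XV (reporting requirements) states for non-serious events: "Only adverse events possibly or definitely related to the study intervention will be reported". The site investigator judges relatedness, and no definitive causal link is needed. Sites are blinded (Protocol VII, Randomization Plan; XIII, Blinding). Serious events are collected whatever their relatedness.

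SAP 7.4 applies the filter at collection, which is "for related non-serious adverse events, and all serious adverse events". The first by-arm summary it lists is "Frequency and percentages of related non-serious and all serious adverse events overall and by intervention group". Later bullets that leave out the word *related* draw on the same collected set. In the closed-session DMC report, Table D1 is related-only for non-serious events, and so is "Table D5. Related Non-Serious Adverse Events by System Organ Class, by Treatment".

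**The checklist.** Protocol Table 1 lists an eight-item interview described as "Systematic review of possible lithium side effects". Table 6 names it as the means of eliciting adverse events and marks it in 13 visit columns, from baseline to the 30-day follow-up. Table 7 continues it after study drug is stopped.

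**Its output.** The only matching SAP table is "Table B11. Side Effects", in section 8.3.2, which is open session only. SAP 8.3 says that open-session tables are not split by treatment. SAP 7.3 lists the follow-up data to be compared by arm and does not mention side effects. SAP 7.1 has a general sentence about tabulating variables by group. SAP 11 points to section 8.3.2 for descriptive characteristics of the cohort.

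**The concern.** The common harms expected of lithium are non-serious symptoms. Protocol XII gives tremor in almost 50% of people starting the drug, increased thirst and urination in 30-50%, weakness in about 30%, and gastrointestinal symptoms in 10-30%. A prescriber weighing lithium for suicide prevention needs the absolute percentage on each arm and the difference.

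The planned by-arm count passes through an individual causality judgment before the arms are compared. In a blinded randomised trial that judgment is not needed, since the comparison itself separates drug effect from background. The data that could avoid the filter are already scheduled for collection, but no by-arm table is specified for them.

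**Working it through.** The documents state no figure for this point, so there is none to reproduce. The arithmetic shows what the filter can and cannot do.

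**Inputs.** From the documents: 931 per arm (Protocol VII) and lithium incidence pL = 50% (tremor, Protocol XII). Assumed, because the documents give neither: placebo incidence pP of 10%, 15% or 30%, and attribution shares between 80% and 100%.

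**Model.** Let s_b be the share of background symptoms judged at least possibly related, and s_c the share of lithium-caused symptoms so judged. Take the lithium-caused excess as pL − pP. With blinding intact, s_b is the same in both arms. Then:

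- reported placebo incidence = s_b × pP
- reported lithium incidence = s_b × pP + s_c × (pL − pP)
- reported risk difference (RD) = s_c × (pL − pP)
- reported risk ratio (RR) = 1 + (s_c / s_b) × (pL − pP) / pP

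The background term cancels from the RD. The RR is unchanged only when s_c = s_b.

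**Results for 50% v an assumed 15%:**

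| s_c | s_b | Lithium % | Placebo % | RD (points) | RR |
|---|---|---|---|---|---|
| 1.00 | 1.00 | 50.0 | 15.0 | 35.0 | 3.33 |
| 1.00 | 0.90 | 48.5 | 13.5 | 35.0 | 3.59 |
| 1.00 | 0.80 | 47.0 | 12.0 | 35.0 | 3.92 |
| 0.90 | 0.90 | 45.0 | 13.5 | 31.5 | 3.33 |
| 0.90 | 0.80 | 43.5 | 12.0 | 31.5 | 3.63 |
| 0.80 | 0.80 | 40.0 | 12.0 | 28.0 | 3.33 |

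Incidence falls in every row with incomplete attribution. In the second row 1.5 points are lost on lithium, about 14 of 931 people. In the fourth row 5 points are lost, about 47 people. The RD falls only when s_c is below 1.

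**Comparison with sampling error.** The loss in RD is (1 − s_c) × (pL − pP). The 95% half-width is 1.96 × √[(pL(1 − pL) + pP(1 − pP)) / 931]. The loss exceeds the half-width when s_c is below 1 − half-width / (pL − pP).

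| pP | True RD | Half-width | Loss at s_c = 0.95 / 0.90 / 0.80 | s_c at which loss = half-width |
|---|---|---|---|---|
| 10% | 40 | 3.75 | 2.0 / 4.0 / 8.0 | 0.906 |
| 15% | 35 | 3.95 | 1.75 / 3.5 / 7.0 | 0.887 |
| 30% | 20 | 4.36 | 1.0 / 2.0 / 4.0 | 0.782 |

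These half-widths assume that all 931 are assessed. Dropout would widen them and lower the thresholds.

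**If side effects reveal the arm.** Background symptoms may then be attributed differently by arm. With 50% v 20%, and overall attribution of 0.90 on lithium and 0.50 on placebo, the reported RD is 0.90 × 50 − 0.50 × 20 = 35 points against a true 30. Blinded attribution cannot produce this, since it would need s_c = 35/30, which is above 1.

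**Detection.** Finding a difference is little affected. For 30% v 20% with 931 per arm, power is 99.9% with full attribution and still 90% if only half of the symptoms in both arms are judged related. The loss is in the size of the estimates.

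**The case against.** The strongest reply is that the filter is weakest for exactly these symptoms. The checklist covers possible lithium effects and is itself the elicitation tool, and *possibly* related is enough. Protocol VIII.F also tells sites, when in doubt, to treat symptoms as excess lithium. A blinded investigator who records new tremor or thirst has little reason to call it not even possibly related. This stands and limits the likely size. It does not remove the filter: VIII.F governs dosing, and XV leaves relatedness to clinical judgment. Protocol VIII.D argues that comorbidity and other medication will obscure lithium's side effects, and the same complexity offers alternative explanations for a symptom.

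A second reply is that SAP 7.1, together with SAP 11's pointer to section 8.3.2 (where Table B11 sits), already implies a by-arm side-effects table in the final report. That is a fair reading but not a secure one. SAP 7.1 is generic, and SAP 11 cites 8.3.2, a section headed baseline assessment, for cohort characteristics. Neither fixes new onset against baseline, visits or denominators. The statement in Protocol XV that all adverse events go on event forms does not widen the set that SAP 7.4 analyses.

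Third, restricted reporting is a stated choice, justified by lithium's known profile, and the trial has no tolerability objective. That explains light adverse event collection. It gives no reason to leave collected checklist data without a by-arm table.

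**Conclusion.** The point holds as a modest, inexpensive improvement. By-arm non-serious events are restricted to those judged related, and the checklist has no explicit by-arm output. Absolute incidence is under-counted to the extent that any symptom is judged unrelated. With blinding intact, the risk difference is reduced only to the extent that lithium-caused symptoms are. The size is unknown: every attribution share and placebo rate above is an assumption, and the true loss may be small.

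Three stronger readings are tempting, and the documents do not support them.

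- **The risk difference shrinks in proportion and the risk ratio is preserved.** This needs one common attribution share for lithium-caused and background symptoms. Blinding does not imply that. With all lithium-caused symptoms captured and 90% of background ones, the difference is intact and the ratio rises from 3.33 to 3.59.
- **The bias always favours lithium.** If side effects reveal the arm, the difference can be inflated.
- **Common harms will be substantially missed.** Nothing in the documents shows low attribution. The thresholds in the second table say when a loss would matter, not that one occurs.

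Serious adverse events are outside the point.

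**What to change.** In SAP 7.4, add a by-arm table of each checklist item regardless of relatedness. Show the percentage with the symptom newly present since baseline (or worse, if the form grades severity), both ever on treatment and by scheduled visit. Give the risk difference with its 95% CI and the number assessed at each visit. Show checklists completed after study drug is stopped separately (Protocol Table 7). Keep the related-event display. Offer the DMC Table B11 by treatment in closed session; Protocol XV leaves the format to the DMC.

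First confirm that item-level answers are in the database and whether severity is graded. The forms are not among the documents, but Table 6 names B13 and T02 for this assessment, a side-effects summary already goes to the coordinating center (Protocol XIII), and Table B11 is planned, so the data appear to be available.

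The cost is SAP wording, a table shell and one more table. That table will be noisier than the related-event display because it includes background symptoms. It will also have missing visits after dropout, which the plan puts at up to 40% (SAP 4.6), so the numbers assessed must be shown beside the percentages.

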10.1. Interim Analysis	
10.2. Futility Analysis	
11. Final Statistical Report.....	page 24
12. References.....	page 25

1. Introduction

This document outlines the statistical methods for the analysis of data collected in the Department of Veterans Affairs Cooperative Studies Programs (CSP) study #590 entitled “A Randomized double-blind placebo-controlled trial of lithium augmentation and enhanced suicide prevention management in preventing suicide re-attempts in individuals with depression and bipolar disorder.” The purpose of this document is to provide guidelines from which the analysis will proceed. Deviations from these guidelines will be documented and filed electronically in the study central file Sharepoint site.

The following documents were used in preparation of this statistical analysis plan (SAP):

- Clinical Study Protocol CSP #590
- Case Report Forms (CRF) from above entitled Protocol
- Global CSP SOP 2.9: “Developing and Conducting Statistical Analyses
- Local Work Instruction WI 201Statistical Analysis Plan and Biostatistical Research Data Processing Plan Creation and Amendment
- Local Job Aid No. 5: Guide to Writing Statistical Analysis Plans

2. Overview of the Study Design and Study Objectives

This is a double-blind, placebo-controlled randomized clinical trial that will assess the effectiveness of lithium augmentation to enhanced usual care for prevention of repeated fatal and non-fatal suicide attempts in participants with bipolar disorder or depression who have survived a recent episode of suicidal self-directed violence.

A total of 1862 subjects recruited from 29 Veterans Health Administration (VHA) centers over a 3 year period are expected to be randomized equally to lithium (Lithium ER) or placebo. Participants will be followed actively for 12 months from randomization. Adverse event monitoring for safety will be for one additional month beyond active follow up, i.e., up to 13 months.

The primary hypothesis is that lithium is superior to placebo for the prevention of episodes of suicidal self-directed violence over time. The primary outcome measure is time from randomization for treatment allocation to any first episode of suicide attempt, interrupted attempt, hospitalization specifically to prevent suicide, or death from suicide.

As secondary objectives of the study, lithium efficacy will be evaluated for prevention of subtypes of suicidal self-directed violence, for all suicidal self-directed violence events (even after the first recurrence), for prevention of repeated events in subgroups as well as in the entire sample, and to identify potential mediators.

The tertiary objectives of the study are to extend the follow up period using electronically available data to describe patterns of lithium use following active participation in the study participants, as well as to evaluate rates and determinants of suicide reattempts and all cause mortality over a longer follow up period.

3. Investigational Plan

